Statistical Analysis Plan

ADVICE: Attenuation of D-dimer using Vorapaxar to target Inflammatory and Coagulation Endpoints

A double blind randomised comparison of vorapaxar versus placebo for the treatment of HIV associated inflammation and coagulopathy in patients with well controlled HIV replication

Protocol Registration Number: NCT02394730

Version 1, 13 November 2017

ADVICE Statistical Analysis Plan

[figure not shown]
The final statistical analysis will be performed when all randomised participants have completed follow-up to week 18, or have permanently stopped trial follow-up, and all data have been entered into the study database, data cleaned and database locked.

1. STUDY POPULATIONS

1.1 Subject Disposition

The disposition of participants will be described by the following diagram (Figure 1).

Figure 1. Patient disposition

1.2 Protocol Violations

Number, proportion and reason for any protocol violations and variations will be described by randomization arm. For this purpose we will report any enrolment event that contravenes an inclusion criterion and/or meets an exclusion criterion, and any event that could potentially affect either the primary endpoint or ongoing patient safety.

1.3 Definition of Populations for Analysis

All endpoints will be analysed using a modified Intention to Treat (mITT) approach.

We will include all randomised participants who received any study drug and had any study follow-up. All available follow-up data will be included, regardless of whether the participant remained on study drug.

Sensitivity analyses based on different study populations for analysis may be considered including:

- mITT last observation carried forward for participants who stopped study follow-up
- per protocol – censoring data at time of stopping trial drug

But given the known excellent trial follow-up, these analyses are not currently thought necessary.

1.4 Summary of Numbers Analyzed

Number of participants contributing data to each study visit according to mITT will be summarized by randomised treatment.

Changes, if any, to participants antiretroviral treatment during the study will also be summarized.

2. EVALUATION OF DEMOGRAPHICS AND BASELINE CHARACTERISTICS

2.1 Demographics and Baseline Characteristics

Participant demographic and baseline characteristics (Table 2), ascertained at time of study enrolment, will be reported by randomization treatment. Continuous variables will be presented as mean and standard deviation (SD), median, 25th, 75th percentile, minimum and maximum value. Categorical variables will be presented as number and percent. Baseline is defined as the date of randomisation, without exception.

No formal statistical tests will be performed to evaluate potential between-group differences at baseline. If there are important imbalances in baseline characteristics, which are both clinically important and related to the primary endpoint, then analyses will be performed and presented

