2.0 Study Flow Chart: Time and events schedule

Study Phase	Screening	Randomisation	Phase 1				Phase 2	
Study week number ^c	SCRN ^a	0 ^b	1	4	8	12	13-17 No study drug	18
Clinical Assessments								
Informed consent	•							
Medical and HIV history	•							
Interim history, AEs assessment and concomitant medication		•	•	•	•	•		•
Targeted physical examination (symptom directed)	•	•	•	•	•	•		•
Vital Signs ^d		•	•	•	•	•		•
Dispense study medication		•		•	•			
Real time local laboratory assessments								
Biochemistry ^e	•	•				•		•
Liver function ^f	•	•				•		•
Haematology ^g	•	•	•	•	•	•		•
Fasted lipids ^h		•						
CD4+ and CD8+ T cell (absolute and %) ⁱ	•	•	•	•	•	•		•
Virology: plasma HIV-1 RNA ^j	•	•	•	•	•	•		•
d-dimer	•							
Pregnancy test ^k	•	•		•	•	•		•
Storage samples for central laboratory analysis								
D-dimer		•	•	•	•	•		•
Hs-CRP		•	•	•	•	•		•
IL-6		•	•	•	•	•		•
Storage samples for central laboratory analysis (exploratory analysis)								
Ultrasensitive plasma viral load		•				•		•
T cell activation marker		•	•	•	•	•		•
ADCC Antibody/ NK cell function		•	•	•	•	•		•
PAR-1 expression ^l		•	•			•		•
Plasma markers of inflammation (sCD14, sCD163)		•				•		•

a All screening assessments are to be completed within 14 days prior to randomisation;

b All randomisation (week 0) assessments should be completed before the participant commences study drugs. Study drug should commence within 1 day of randomisation;

c Study Week Number: All efforts should be made to schedule visits in keeping with the proposed week numbers. Phase 1: week 1 to be conducted within 13 days of randomisation, weeks 4, 8 and 12 to be done +/- 2 weeks of scheduled visit date. Phase 2: week 18 to be conducted within + 2 weeks of scheduled visit date.

d Vital Signs: Sitting blood pressure (all visits), height (week 0 only) and weight (week 0 and week 18 only);

e Biochemistry: electrolytes (sodium, potassium, calcium, bicarbonate, chloride, phosphate), creatinine, urea;

f Liver Function test: ALT and AST;

g Haematology: haemoglobin, white blood cells, neutrophils, lymphocytes, platelets to be done (day 0 and week 12 to be done as standard of care). Haemoglobin to be tested at the time of any clinically significant bleeding event (clinical judgement to be used);

h Fasting lipid parameters includes: total cholesterol, HDL cholesterol, calculated LDL cholesterol and triglycerides;

i CD4+ and CD8+ cell counts: Day 0 and week 12 to be done as standard of care;

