9.1.2 Laboratory assessments at screening

- If the patient is female and is of child bearing potential, she must have a urine or blood sample pregnancy test
- Serum chemistries and liver function tests: electrolytes (sodium, potassium, bicarbonate, chloride, phosphate), urea, creatinine and LFTs (ALT and AST only)
- Assessment of renal function will be undertaken with derivation of creatinine clearance using the CKD-EPI (Chronic Kidney Disease Epidemiology Collaboration) equation:

Estimated GFR = $141 \times \min(\text{SCR}/\kappa, 1)^\alpha \times \max(\text{SCR}/\kappa, 1)^{-1.209} \times 0.993^{\text{Age}^e} \times (1.018 \text{ if female} \times (1.159 \text{ if black}))$

- Haematology: full blood count (haemoglobin, white cells, neutrophils, lymphocytes, platelets)
- Plasma HIV-RNA analysis
- Immunology: CD4 and CD8 (% and absolute)
- Plasma d-dimer

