13.7 Plasma d-dimer determination

Plasma d-dimer will be measured at the local laboratory for assessment of eligibility. Plasma samples at weeks 0, 1, 4, 8, 12 and 18 will be stored and sent to a central laboratory (LEIDOS Biomedical Research Inc. in the USA) for central assessment of d-dimer, IL-6 and Hs-CRP at the end of the study. These central results will be used for the analysis of the study. Results cannot be provided in real time to individual patients. Results will be provided at completion of the project.

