4. EVALUATION OF PRIMARY AND SECONDARY EFFICACY ENDPOINTS

4.1 Primary Endpoint

The primary endpoint is changes in log₁₀ d-dimer from baseline (week 0) to the average of weeks 8 and 12.

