4.3 Statistical analysis

All efficacy endpoints will be summarised by randomised treatment and study visit. Continuous measures will be summarised as means and standard deviations, categorical measures as n and percent.

Formal statistical comparisons between randomised treatment arms will use repeated measures regression methods as appropriate to continuous and binary data. Precise models to be used will depend on data and fit to model assumptions, but *a priori* choice will be generalised estimating equations with robust standard errors. Initial analyses will be unadjusted comparison of randomised treatments with baseline value only as a covariate, but further adjusted analyses may be performed as needed.

Further regression modelling may be performed to explore how primary and secondary activation and coagulation endpoints evolve over time.

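### For CD4 and CD8, a baseline fixed to the randomisation date leaves a comparable screening value unused and has no fallback: a minor point that SAP wording can mend

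*SAP*

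**What the plan says.** SAP 2.1: "Baseline is defined as the date of randomisation, without exception". It names a date. It gives no window, no pre-dose condition and no rule for a missing value.

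SAP 4.3: "Initial analyses will be unadjusted comparison of randomised treatments with baseline value only as a covariate, but further adjusted analyses may be performed as needed".

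The Protocol's flow chart (section 2.0) lists CD4 and CD8 under local laboratory assessments at screening and at week 0. Protocol 9.1.2 and 9.2.2 repeat this, and screening falls within 14 days before randomisation. A flow-chart footnote adds: "CD4+ and CD8+ cell counts: Day 0 and week 12 to be done as standard of care". Protocol 13.1 tolerates blood taken two to three days from the visit date, and Protocol 9.2 requires all week-0 evaluations before study drug.

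D-dimer is handled differently. Protocol 13.7 says "Plasma d-dimer will be measured at the local laboratory for assessment of eligibility", and "Plasma samples at weeks 0, 1, 4, 8, 12 and 18 will be stored and sent to a central laboratory"; the analysis uses the central results. SAP 4.1 defines the primary endpoint as "changes in log₁₀ d-dimer from baseline (week 0) to the average of weeks 8 and 12".

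**The concern.** A single CD4 or CD8 count carries within-person noise, and the trial has about 28 to 30 participants per arm. A second pre-treatment count of the same kind is already collected. Because it precedes randomisation, using it as a covariate cannot bias the arm comparison. Leaving it out gives up some precision on the four CD4/CD8 endpoints in SAP 4.2.

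The second issue is coverage. A sample drawn the day before randomisation is acceptable under Protocol 13.1 but, taken literally, is not a baseline under SAP 2.1. A participant with no baseline has no change score and falls out of a baseline-adjusted model. That sits badly with SAP 1.3, which intends to use all available follow-up data.

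**Working it through.** **The plan's own figure.** Inputs from Protocol 6.1: SD of change 0.4, correlation of the two changes 0.5, 28 per arm. The two-sided 5% level is from 6.2.1.
- SD of the mean of two changes = 0.4 × √((1 + 0.5)/2) = 0.3464.
- SE of the arm difference = 0.3464 × √(2/28) = 0.0926.
- Power at 0.26 = Φ(0.26/0.0926 − 1.96) = 80.2%; at 0.30 it is 90.0%.

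The stated 80% and 90% reproduce. They concern d-dimer change scores without a covariate, so they do not depend on a second baseline. No power is planned for CD4 or CD8.

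**Which markers have two comparable pre-treatment values**
- CD4 and CD8: yes, both local.
- HIV RNA: measured twice, but the endpoint is a proportion below 50 copies/mL with no change score.
- Haematology, chemistry and liver tests: measured twice, but SAP 5.2 summarises laboratory results as graded events, not in baseline-adjusted models.
- D-dimer: local at screening, central at week 0.
- hs-CRP, IL-6, sCD14, sCD163 and PAR-1: no screening sample.

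**Precision for CD4/CD8, equal correlation.** Let r be the correlation between any two visits (assumed; not in the documents). With unit variance, the residual variance is 1 − r² with one pre-treatment value and 1 − 2r²/(1 + r) with the mean of two. The ratio simplifies to (1 + 2r)/(1 + r)².

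| r | variance ratio | SE ratio | interval narrower by |
|---|---|---|---|
| 0.6 | 2.2/2.56 = 0.859 | 0.927 | 7% |
| 0.7 | 2.4/2.89 = 0.830 | 0.911 | 9% |
| 0.8 | 2.6/3.24 = 0.802 | 0.896 | 10% |
| 0.9 | 2.8/3.61 = 0.776 | 0.881 | 12% |

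**If correlation decays with time.** Screening and week 0 are closer together than either is to week 12, so equal correlation flatters the proposal. A covariance made of a stable, a decaying and a noise component (sizes assumed), at weeks −2, 0 and 12, gives a variance fall of about 6% to 9%. Since √0.94 = 0.970 and √0.91 = 0.954, intervals narrow by about 3% to 5%.

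A hand check brackets this. Let a be the correlation of screening with week 0, c that of week 0 with follow-up, and d that of screening with follow-up. The mean of the two explains (c + d)²/(2(1 + a)) of the variance. With c = d = 0.7:
- a = 0.8: 1.96/3.6 = 0.544, and 0.456/0.51 = 0.893, an 11% fall.
- a = 0.9: 1.96/3.8 = 0.516, and 0.484/0.51 = 0.949, a 5% fall.

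The mean helps only if d/c exceeds √(2(1 + a)) − 1, which is 0.90 at a = 0.8 and 0.95 at a = 0.9. The screening value must therefore predict follow-up nearly as well as week 0 does.

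**The outcome must match the covariate.** Under equal correlation, modelling change from week 0 alone with the mean as covariate adds (1 − r)/2 to the residual variance. At r = 0.8 that is 0.289 + 0.100 = 0.389, worse than 0.360 with one baseline. The model should take the follow-up value, or change from the same mean, as outcome.

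**Missing week-0 values.** Each participant lost is 1/60 = 1.7% of the sample. Neither document reports how many lack a week-0 value.

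**The case against.** The strongest reply is that one pre-dose week-0 value is a valid, unbiased baseline, and that fixing it firmly prevents choosing between values later. That stands. The point is an improvement, not a correction of an error, and any new rule must be equally fixed in advance.

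A reader might infer more than the documents support:
- *That the primary endpoint discards half of its pre-treatment information.* It does not. Central d-dimer starts at week 0. The screening value is a local result, participants were selected on it, and it may be in fibrinogen equivalent or d-dimer units. The entry thresholds of 200 and 100 ng/mL differ by a factor of 2, or 0.301 log₁₀, more than the 0.26 target. In a simulation with half of those screened passing, averaging the screening value into baseline moved mean change by 0.05 to 0.08 log₁₀ in both arms.
- *That participants are being lost.* Week-0 evaluations must precede study drug (Protocol 9.2), and randomisation follows their completion (9.2.3). The standard-of-care footnote does not say that the test may fall on another day. Loss is a possibility under a literal reading. SAP 4.1 itself equates baseline with week 0. For central markers, screening could not fill a gap anyway.
- *That no other adjustment is allowed.* SAP 4.3 permits further adjusted analyses, and Protocol 6.2.1 plans models with key baseline covariates. Neither names the screening value.
- *That every local test should be averaged.* Creatinine and eGFR grades in Protocol Appendix 1 depend partly on change from baseline, so averaging would alter safety grading without any gain in a model.

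**Conclusion.** The point holds as a minor, cheap improvement limited to CD4 and CD8. Four of the 18 secondary endpoints in SAP 4.2 could be estimated with intervals about 3% to 5% narrower if correlation decays, and 7% to 12% narrower at best. Both ranges rest on assumed correlations and on both pre-treatment values being available. Steep decay could remove the gain from averaging.

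Separately, SAP 2.1 and Protocol 13.1 do not fit together if read literally, and a missing week-0 value has no rule. That part needs no assumption about correlation, but its effect on this trial cannot be sized from the documents. No gain is claimed for the primary endpoint, and its planned power is unaffected.

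**What to change.** Before treatment codes are released:

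1. Replace the sentence in SAP 2.1 with: *Baseline is the week-0 pre-dose value, including samples taken within the leeway of Protocol 13.1; for locally measured tests, if the week-0 value is missing, the screening value is used.*
2. In SAP 4.3, for the CD4 and CD8 models only, use the mean of the screening and week-0 values (or the one available) as the baseline covariate, with the follow-up value, or change from that same mean, as outcome.
3. Keep the central week-0 sample as baseline for d-dimer, hs-CRP, IL-6, sCD14 and sCD163. Do not average haematology or chemistry baselines used for DAIDS grading. Screening d-dimer, put on a common unit scale, is at most an optional sensitivity covariate.

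The cost is SAP wording and a few lines of programming, with no new samples or participants. The downside is that the model baseline for CD4/CD8 is defined differently from that of the other markers, which the report should state.

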4. EVALUATION OF PRIMARY AND SECONDARY EFFICACY ENDPOINTS

4.1 Primary Endpoint

The primary endpoint is changes in log₁₀ d-dimer from baseline (week 0) to the average of weeks 8 and 12.

4.2 Secondary Endpoints

Virologic measures

- Proportion of participants in each treatment group with plasma HIV-1 RNA <50 copies/mL at week 12 and week 18

Immunologic measures

- Differences between treatment groups in mean change from baseline in CD4+ cell counts at week 12
- Differences between treatment groups in mean change from baseline in CD4+ cell counts at week 18
- Differences between treatment groups in mean change from baseline in CD8+ cell counts at week 12
- Differences between treatment groups in mean change from baseline in CD8+ cell counts at week 18

Activation/Coagulation measures of interest

- Percentage of patients in each treatment group with d-dimer <165ng/mL at week 8 and week 12
- Percentage of patients in each treatment group with d-dimer >165ng/mL at week 18
- Differences between treatment groups in mean change from baseline log₁₀ d-dimer at week 18
- Differences between treatment groups in mean change from baseline log₁₀ hs-CRP to the average of week 8 and week 12
- Differences between treatment groups in mean change from baseline log₁₀ hs-CRP at week 18
- Differences between treatment groups in mean change from baseline log₁₀ IL-6 to the average of week 8 and week 12
- Differences between treatment groups in mean change from baseline log₁₀ IL-6 at week 18
- Differences between treatment groups in mean change from baseline log₁₀ sCD14 to the average of week 8 and week 12
- Differences between treatment groups in mean change from baseline log₁₀ sCD14 at week 18
- Differences between treatment groups in mean change from baseline log₁₀ sCD163 to the average of week 8 and week 12
- Differences between treatment groups in mean change from baseline log₁₀ sCD163 at week 18

Immunopathogenesis measures

- Differences between treatment groups in mean change from baseline in percent total CD4 cells expressing PAR-1 at week 12

- Differences between treatment groups in mean change from baseline in percent total CD8 cells expressing PAR-1 at week 12

4.3 Statistical analysis

All efficacy endpoints will be summarised by randomised treatment and study visit. Continuous measures will be summarised as means and standard deviations, categorical measures as n and percent.

Formal statistical comparisons between randomised treatment arms will use repeated measures regression methods as appropriate to continuous and binary data. Precise models to be used will depend on data and fit to model assumptions, but *a priori* choice will be generalised estimating equations with robust standard errors. Initial analyses will be unadjusted comparison of randomised treatments with baseline value only as a covariate, but further adjusted analyses may be performed as needed.

Further regression modelling may be performed to explore how primary and secondary activation and coagulation endpoints evolve over time.

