6.1 Sample size determination

Assumptions are based on data from the STEAL trial¹⁴. Excluding patients with d-dimer < 200 ng/mL, the standard deviation in change in log₁₀ d-dimer is 0.356 at week 12 and 0.414 at week 24. The correlation of these two endpoints is 0.5726.

Using a repeated measures regression analysis at week 8 and 12, variability in change in log₁₀ d-dimer = 0.4, and correlation between these two time points as 0.5 (STEAL trial¹⁴), then a total sample size of 56 patients (2x28) gives 80% (90%) power to detect a mean difference of 0.26 (0.30) logs. A total of 60 patients gives some modest allowance for non-completion.

Mean baseline d-dimer in STEAL¹⁵ (excluding patients with d-dimer < 200 ng/mL at baseline) was 430 ng/mL. Mean log₁₀ decrease in STEAL was 0.07 logs, which corresponds to about a 15% decrease – i.e. in the control arm we might expect a decrease from 430 to about 370 ng/mL. We are powered to detect log differences of the order of 0.26, so in total in the vorapaxar arm we expect a 0.33 log decrease – i.e. a decrease from 430 to about 200 ng/mL. In absolute terms we have 80% power to detect a difference in d-dimer changes of around 170 ng/mL.

These are quite large effect sizes, both compared with the expected variability (0.75 standard deviations), and in absolute terms (differences in d-dimer changes of around 170 ng/mL from expected baseline mean of 430 ng/mL). However, we believe that such large effects would be clinically significant, and will be required to justify expanded studies of vorapaxar treatment in HIV-positive individuals.

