6.2 Analysis Plan

6.2.1 Statistical analysis

Baseline characteristics will be summarised by randomised group. Patients failing to complete study drug will be listed, with accompanying reasons. The primary endpoint will be mean changes in log₁₀ d-dimer levels from baseline at weeks 8 and 12. The proportion of patients with d-dimer < 165 ng/mL will also be summarised.

Mean or median changes, or percentages, as appropriate, in primary and secondary endpoints will be plotted by study week.

Formal analyses will compare the randomised treatment arms in terms of mean differences in changes in log₁₀ d-dimer at week 8 and week 12 using repeated measures regression methods. Models will be fitted using maximum likelihood methods using robust standard errors. Simple unadjusted models will initially be used to estimate the difference between randomised treatment arms in mean changes in log₁₀ d-dimer. Models adjusted for key baseline covariates will also be fitted. If there is overall evidence of a difference between randomised treatment arms at $2p < 0.05$, then further sensitivity analyses will also be performed using simple two-sample (t-test or rank-sum test) applied to the mean change in log₁₀ d-dimer at weeks 8 and 12.

Similar longitudinal methods will also be used to analyse mean changes from baseline in, or proportions of, secondary endpoints at weeks 8 and 12.

Differences between randomised treatment arms in mean changes in, or proportions of, all endpoints at week 18 will be investigated using linear regression or logistic regression methods.

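### Protocol and SAP start from different primary models, the SAP lets its default be replaced on unstated criteria, and neither document says which result decides the primary endpoint.

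*SAP*

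**What the plan says.** - **Protocol 6.2.1** plans repeated measures regression on changes in log10 d-dimer at weeks 8 and 12, fitted by maximum likelihood with robust standard errors. "Simple unadjusted models will initially be used to estimate the difference between randomised treatment arms" in mean change. Models adjusted for key baseline covariates, which are not named, are also planned. The only significance threshold in either document is here, as the condition for t-test or rank-sum sensitivity analyses: "If there is overall evidence of a difference between randomised treatment arms at $2p < 0.05".
- **SAP 4.1** defines the primary endpoint as change from week 0 to the average of weeks 8 and 12.
- **SAP 4.3** says "Precise models to be used will depend on data and fit to model assumptions". The same sentence then gives GEE with robust standard errors as the a priori choice. Next: "Initial analyses will be unadjusted comparison of randomised treatments with baseline value only as a covariate", with further adjusted analyses possible if needed.
- **SAP 2.1** foresees additional analyses: "If there are important imbalances in baseline characteristics, which are both clinically important and related to the primary endpoint". The rest of that sentence is incomplete in the available text.
- **Protocol 5.6 and SAP 4.4** make exploratory analyses conditional on a positive primary result. Neither gives a p-value.
- **Protocol 6.3** rules out adjustment for multiple comparisons.

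**The concern.** The two documents lead with different models for the same endpoint. The SAP calls its model unadjusted although it contains baseline d-dimer, and it does not say that it replaces the protocol's model. Its default can also be exchanged after the data are seen, with no criterion for the exchange.

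In a randomised trial both models estimate the same treatment effect. In a given sample, though, the two estimates differ by the fitted baseline slope times the chance baseline difference between arms, and their standard errors differ too. With about 30 people per arm they can fall on opposite sides of 0.05. If the choice between them is made with results in view, the false-positive rate exceeds the nominal 5%. A reader of the final report could not tell from the plan which result was meant to count.

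**Working it through.** **Inputs from the documents.** Protocol 6.1 gives "variability in change in log₁₀ d-dimer = 0.4", "correlation between these two time points as 0.5", and "then a total sample size of 56 patients (2x28) gives 80% (90%) power to detect a mean difference of 0.26 (0.30) logs". Two-sided 0.05 is taken from Protocol 6.2.1.

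**Input not in the documents.** rho, the correlation between baseline log10 d-dimer and the average of the two changes. It is assumed to lie between 0 and -0.7.

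**Step 1: reproduce the stated power.** The SD of the average of two changes is 0.4 × sqrt((1 + 0.5)/2) = 0.3464. The standard error of the difference with 28 per arm is 0.3464 × sqrt(2/28) = 0.0926.
- At 0.26 logs: 0.26/0.0926 = 2.81; 2.81 - 1.96 = 0.85; power 80.2%.
- At 0.30 logs: 0.30/0.0926 = 3.24; 3.24 - 1.96 = 1.28; power 90.0%.

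Both match the protocol. A t-based calculation gives 78.8% and 88.9%. No baseline-covariate term enters, so the stated power belongs to the unadjusted change-score model.

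**Step 2: power with baseline as a covariate.** The residual SD is 0.3464 × sqrt(1 - rho²), used in the same formula with 28 per arm.

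| rho | Residual SD | Power at 0.26 | Difference detectable with 80% power |
|---|---|---|---|
| 0 | 0.3464 | 80.2% | 0.259 |
| -0.3 | 0.3305 | 83.7% | 0.247 |
| -0.5 | 0.3000 | 90.0% | 0.225 |
| -0.7 | 0.2474 | 97.6% | 0.185 |

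With the 30 per arm actually planned, simulated power at 0.26 is about 81% unadjusted and about 80% to 97% adjusted.

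**Step 3: how far the two tests part.** Trials were simulated with 28 per arm, normal data and complete follow-up (40,000 with no effect and 20,000 with a true 0.26-log difference per setting). The average change was tested with and without baseline as a covariate. Model-based means ordinary standard errors with a t reference. Robust means the uncorrected sandwich with a normal reference.

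| rho | No effect: either p<0.05, model-based | No effect: either p<0.05, robust | True 0.26: tests disagree, model-based |
|---|---|---|---|
| 0 | 5.6% | 6.8% | 2.6% |
| -0.3 | 6.4% | 7.8% | 7.6% |
| -0.5 | 7.2% | 8.8% | 12.9% |
| -0.7 | 8.3% | 10.0% | 18.2% |

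Each model-based test alone stays at 4.8% to 5.2%. Each robust test alone runs at about 5.7% to 6.4%, so part of the robust column comes from the small sample and not from having two models. At 30 per arm the upper end of the model-based null column is 8.4%. Over both sample sizes the ranges are about 5.6% to 8.4% for the null and about 2% to 18% for disagreement.

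**Step 4: where in the range.** Suppose variance is equal at all visits and every pair of visits has correlation r. The two changes then correlate at 0.5, as the protocol assumes, and rho = -sqrt((1 - r)/1.5). For r = 0.3, 0.5 and 0.7 this gives rho of about -0.68, -0.58 and -0.45, the upper half of the table. Smaller baseline variance would move rho towards 0.

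**The case against.** The strongest reply is that the SAP, the dedicated analysis document, already supplies both a default and an order: GEE, robust standard errors, baseline as the only covariate, and anything else described as further and optional. SAP 4.3 also covers every continuous and binary efficacy endpoint, so dependence on data may partly mean data type. This stands as far as it goes: it would be wrong to infer that the SAP has no primary model. What remains is that the default may be replaced on unstated criteria, and that nothing says it decides the endpoint or supersedes the protocol's model.

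Other points that stand:
- A reader might infer that the protocol ignores baseline d-dimer. It does not: the outcome is change from baseline, and adjusted models are planned as well.
- A reader might count the t-test and rank-sum analyses as extra routes to significance. Protocol 6.2.1 allows them only after 2p<0.05, so as written they cannot rescue a null result, and they are left out of the figures above.
- SAP 2.1 does not say that the relation to the endpoint is judged from trial outcomes, and its sentence is incomplete in the available text. No weight is put on it.
- The gate matters less than it looks, because SAP 4.2 already lists sCD14, sCD163 and PAR-1 expression as secondary endpoints without a condition.
- Eligibility requires local screening d-dimer above 200 ng/mL, which may shrink baseline variance. With baseline variance assumed to be half that at follow-up and 30 per arm, the either-test rate is 5.4% to 7.2% and disagreement at 0.26 is 2% to 11%.

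**Conclusion.** The concern holds in a limited form. The documents give two different first models, the SAP allows its own to be replaced after the data are seen, and no text identifies the deciding result. That 2p<0.05 is the trial's decision threshold is itself an inference: it appears once, in the protocol, as a trigger for sensitivity analyses, and the SAP states no alpha.

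The cost is a null either-test rate of at most about 5.6% to 8.4% (about 7% to 10% with uncorrected robust standard errors) and disagreement between the tests in about 2% to 18% of trials at the design difference. These figures rest on the assumed rho, normal data, complete follow-up and two models only. It would be too strong to conclude that the trial's type I error is 8% or 10%: that would need the smaller p-value always to be reported, and the plan does not say it will be.

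The sample size is sound under either model. Apart from a trivial loss when rho is near 0, baseline adjustment keeps or raises power.

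**What to change.** In SAP 4.3, delete "Precise models to be used will depend on data and fit to model assumptions" as it applies to the primary endpoint. State that:
- the single primary test is the baseline-adjusted GEE comparison of log10 d-dimer change averaged over weeks 8 and 12, at two-sided 0.05;
- its working correlation and a small-sample correction to the robust standard error are specified in advance;
- this test alone decides whether the primary endpoint is reached, and so whether the exploratory analyses open;
- the unadjusted model, models adjusted for imbalanced covariates and alternative model forms are sensitivity analyses, reported whatever the primary result.

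Align Protocol 6.2.1 with this text. The small-sample correction is needed because naming one test does not by itself bring an uncorrected robust test back from about 6% to 5%.

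The cost is wording, agreed before unblinding, with no change to sample size or data collection. The sponsor gives up the freedom to change the primary model after seeing the data.
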